6. STATISTICAL ANALYSES

Note that standard data derivation rule and stat methods are described in [Annex 1 standard data derivation rule and statistical methods](#) and will not be repeated below.

6.1. Demography

6.1.1. Analysis of demographics/baseline characteristics planned in the protocol

The analysis of demography will be performed on the ES and on the PPS for immunogenicity.

Demographic characteristics such as age at vaccination in years, race, ethnicity, vital signs and cohort description will be summarised by group using descriptive statistics:

- Frequency tables will be generated for categorical variable such as race.
- Mean, median, standard error and range will be provided for continuous data such as age.

The distribution of subjects will be tabulated as a whole and per group and for each age category (18 - 32 years and 33 - 45 years).

Withdrawal status will be summarised by group using descriptive statistics:

- The number of subjects enrolled into the study as well as the number of subjects excluded from PPS analyses will be tabulated.
- The number of withdrawn subjects will be tabulated according to the reason for withdrawal.

6.2. Immunogenicity

6.2.1. Analysis of immunogenicity planned in the protocol

The analysis will be performed on the applicable PPS cohort for immunogenicity and, if in any group the percentage of vaccinated subjects with serological results excluded from the PPS for analysis of immunogenicity is $\geq 5\%$, a second analysis will be performed on the ES.

6.2.1.1. Within group analysis*Humoral Immune response to RSV vaccine*

For each group, at each timepoint that blood samples are collected and for each assay (unless specified otherwise):

- GMTs/GMCs will be tabulated with 95% CI based on log-transformed values and represented graphically.
- Percentage of subjects above the seropositivity threshold will be tabulated with exact 95% CI.

Percentage of subjects above the seropositivity threshold and GMTs/GMCs will also be tabulated by group for each age category (18 - 32 years and 33 - 45 years).

- Pre- and post-vaccination antibody titres/concentrations will be displayed using reverse cumulative curves.
- The distributions of **neutralising** antibody titres will be tabulated in the tables with log₂ scale (< 7, 7-8, > 8-9, > 9-10, > 10-11, > 11-12, > 12 log₂).
- Percentage of responders in terms of **neutralising** antibody titres will be tabulated with exact 95% CI.
- Individual post-vaccination *versus* pre-vaccination results will be plotted using scatter plots. Results of the control group will be used as a reference.
- Geometric mean of ratios of antibody titres/concentrations at each post-vaccination timepoint over pre-vaccination will be tabulated with 95% CI.
- ***Distribution of the fold increase of the antibody titres/concentrations will be tabulated:***
 - ***For neutralising antibody titres against RSV-A and RSV-B: percentage of subjects with a fold increase equal to or above 1, 2, 2.5, 3, 4, 6, 8 10, 11 and 12 by pre-vaccination titre category: <7, 7-8,]8-9,]9-10,]10-11,]11-12, >12 log₂, and cumulative: <7, ≥7, ≥8, ≥9, ≥10, ≥11, ≥12 log₂.***
 - ***For antibody concentrations against NEO: percentage of subjects with a fold increase equal to or above 1, 1.5, 2, 2.5, 3, 3.5, 4, 4.5 and 5.***

The kinetics of individual antibody titres/concentrations will be plotted as a function of time for subjects with results available at all timepoints.

- An analysis of variance model for repeated measures will be fitted to calculate GMTs/GMCs with treatment group, visit and their interaction as fixed effects if necessary.

If deemed necessary, the same analyses may be done by age category (18 - 32 years and 33 - 45 years).

6.2.1.2. Between group assessment

Exploratory comparisons will be performed for RSV neutralising antibody titres and PCA concentrations post-vaccination (Day 30, Day 60 and Day 90) between the different RSV vaccine groups.

- Estimation of GMT/GMC ratios between groups with corresponding 95% CI using an ANCOVA model on the logarithm10 transformation of the titres/concentrations. If a statistically significant difference is found ($p < 0.05$), pairwise comparisons will be made using Tukey's multiple comparison adjustment. This model includes:
 - The vaccine group as the fixed effect
 - The pre-vaccination titre/concentration as the covariate
 - Age groups (18-32 years and 33-45 years) and center as the categorical covariate if deemed necessary
- GMT/GMC ratios with corresponding 95% CI will be computed between the RSV vaccine groups
 - PreF-120 *minus* PreF-30
 - PreF-120 *minus* PreF-60
 - PreF-60 *minus* PreF-30

6.2.2. Additional considerations

In order to add the analysis of the anti-RSV F IgG Total and IgG1 subclass tested at Day 0 and Day 30 in a random subset of 50 subjects per group. The following analysis will be performed on the Per-Protocol Set (PPS) for analysis of immunogenicity for each group and for both assays:

- *GMCs with 95% CI will be tabulated.*
- *Percentage of subjects above the seropositivity threshold will be tabulated with exact 95% CI.*
- *Geometric mean of ratios of antibody concentrations at each post-vaccination timepoint over pre-vaccination (fold increase) will be tabulated with 95% CI, and represented graphically.*
- *Individual ratios of antibody concentrations will be displayed using reverse cumulative curves.*
- *Exploratory comparisons between groups: geometric mean ratios and 95% CIs of fold increase post/pre between the RSV groups:*
 - *120 PreF versus 60 PreF*
 - *120 PreF versus 30 PreF*
 - *60 PreF versus 30 PreF*

This will be performed using an ANOVA model on the logarithm10 transformation of the concentrations including the vaccine group as covariates. If a statistically significant difference is found ($p < 0.05$), pairwise comparisons will be made using Tukey's multiple comparison adjustment.

In addition, the following immunogenicity analysis will be performed in the subset of subjects with IgG/IgG1 data available:

- *GMCs will be tabulated with 95% CI for anti-RSV A and anti-PCA*
- *Percentage of subjects above the seropositivity threshold will be tabulated with exact 95% CI for anti-RSV A and anti-PCA.*

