- *All CI computed will be two-sided 95% CI.*

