60 PreF = 60 µg PreF
120 PreF = 120 µg PreF
Control = Placebo

Note: This graph is provided as an example. This graph will display the 4 groups and the 4 immuno timepoints: PRE, PI(D30), PI(D60) and PI(D90)

Template 52 GM of individual ratios (fold increase post over pre) and their 95% CIs for anti-RSV F IgG1 and IgG total antibody assays and each group, at <Day xx> (Per protocol set)

30 PreF = 30 µg PreF
 60 PreF = 60 µg PreF
 120 PreF = 120 µg PreF
 Control = Placebo

Note: this graph is provided as an example. It will be adapted to display IgG total and Ig1 only, and the 4 groups: 30 PreF, 60 PreF, 120 PreF, Control.

Template 53 Exploratory comparisons (GM ratios of fold increase post/pre) between RSV groups with corresponding 95% confidence interval for anti-RSV F antibody concentrations (IgG Total) at Day 30 (Per protocol set)

								GMF ratio			
								Tukey's 95% CI			
Antibody	Timepoint	Group description	N	GMF	Group description	N	GMF	Ratio order	Value	LL	UL
anti-RSV F antibody (IgG Total)	PI(D30)	120 PreF			60 PreF			120 Pre/60 PreF			
		120 PreF			30 PreF			120 PreF/30 PreF			
		60 PreF			30 PreF			60 PreF/30 PreF			

30 PreF = 30 µg PreF

60 PreF = 60 µg PreF

120 PreF = 120 µg PreF

Antibody concentration estimated by the ANOVA model

GMF = Geometric mean of fold increase

N = Number of subjects with pre-vaccination results available

Tukey's 95% CI = 95% confidence interval for the GMF ratio (ANOVA model, Tukey's adjustment), LL = lower limit, UL = upper limit

Pvalue of ANOVA model at PI(D30) is: xxxx

PI(D30) = Post-vaccination at Day 30

Template 54 Comparisons of GM ratios with corresponding 95% confidence interval between anti-RSV F antibody concentrations (IgG Total) and anti-RSV-A neutralising antibody titers at pre-vaccination (Per protocol set)

									GM ratio		
				95% CI					95% CI		
Timing	Group description	N	IgG Total GMC	LL	UL	RSV-A neut GMT	LL	UL	Value	LL	UL
PRE(D0)	<each group>										
PRE(D0)											
PRE(D0)											
PRE(D0)											

<each group>:

30 PreF = 30 µg PreF

60 PreF = 60 µg PreF

120 PreF = 120 µg PreF

Control = Placebo

N = Number of subjects with available results at Day30 and pre-vaccination for IgG Total and RSV-A neut

GMC = Geometric mean antibody concentration calculated on all subjects for IgG Total

GMT = Geometric mean antibody titre calculated on all subjects for RSV-A neut

GM Ratio=Geometric mean of individual ratio of IgG Total to RSV-A neut for each group

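### The IgG Total/IgG1 comparison targets ratios of fold increase but specifies a group-only ANOVA on concentrations, and leaves out the measured Day 0 value as a covariate

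*SAP*

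**What the plan says.** SAP Amendment 4, section 6.2.2, adds IgG Total and IgG1 assays, "tested at Day 0 and Day 30 in a random subset of 50 subjects per group". For the three pairs of RSV groups it announces "geometric mean ratios and 95% CIs of fold increase post/pre between the RSV groups". The model follows directly: "This will be performed using an ANOVA model on the logarithm10 transformation of the concentrations including the vaccine group as covariates". Vaccine group is the only term named. A gatekeeping step comes next: "If a statistically significant difference is found ($p < 0.05$), pairwise comparisons will be made using Tukey's multiple comparison adjustment". The same model sentence stands in Amendments 2 and 3.

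Template 53 shows the geometric mean fold increase (GMF) per group and a GMF ratio, with the interval described as "95% confidence interval for the GMF ratio (ANOVA model, Tukey's adjustment". Another footnote line in the same template says that what the ANOVA estimates is the antibody concentration.

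For neutralising titres and PCA, section 6.2.1.2 plans differently: "Estimation of GMT/GMC ratios between groups with corresponding 95% CI using an ANCOVA model on the logarithm10 transformation of the titres/concentrations". Its terms are vaccine group, "The pre-vaccination titre/concentration as the covariate", and age group and centre where deemed necessary.

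**The concern.** There are two separate faults.

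- **Outcome and target differ.** A group-only ANOVA on Day 30 concentrations gives a ratio of Day 30 GMCs. The announced quantity is a ratio of fold increases. Within a sample the two differ by exactly the ratio of the Day 0 GMCs, so a programmer following the sentence and one following the table title would report different numbers.
- **Day 0 is not a covariate.** An ANOVA on log fold increase uses Day 0 only by subtracting it in full, which is efficient only when the slope of Day 30 on Day 0 is 1. An ANOVA on Day 30 concentration does not use it at all. The SAP gives no reason for treating IgG differently from neutralising titres and PCA.

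At stake is the precision of a comparison with at most 50 subjects per group, and how far a chance baseline difference moves the reported ratio.

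**Working it through.** The SAP gives no standard deviation, correlation, power or precision target for this comparison, so there is no planned figure to reproduce.

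**Inputs from the SAP.** n = 50 per group; Day 0 and Day 30 both tested; intervals per section 11.2.4: "All CI computed will be two-sided 95% CI".

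**Assumptions.** Equal SD (s) of log10 concentration at Day 0 and Day 30; Day 0/Day 30 correlation ρ from 0.3 to 0.9.

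**Step 1: residual variance under each model**

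- ANOVA on log10 Day 30 concentration: s²
- ANOVA on log10 fold increase: 2s²(1 − ρ)
- ANCOVA with log10 Day 0: s²(1 − ρ²)

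ANCOVA relative to fold-increase ANOVA is (1 − ρ²) / [2(1 − ρ)] = (1 + ρ)/2. Relative to concentration ANOVA it is 1 − ρ².

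| ρ | ANCOVA / fold-increase ANOVA | ANCOVA / concentration ANOVA |
|---|---|---|
| 0.3 | 0.65 (35% less) | 0.91 (9% less) |
| 0.5 | 0.75 (25% less) | 0.75 (25% less) |
| 0.7 | 0.85 (15% less) | 0.51 (49% less) |
| 0.9 | 0.95 (5% less) | 0.19 (81% less) |

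A simulation of 4,000 two-group trials per ρ gave the inverse ratios as 1.52, 1.35, 1.17 and 1.04 (fold increase) and 1.09, 1.33, 1.97 and 5.11 (concentration). The algebra gives 1.54, 1.33, 1.18 and 1.05, and 1.10, 1.33, 1.96 and 5.26.

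**Step 2: an example.** Assume s = 0.4 log10, a true ratio of 1.5, n = 50 per group, two-sided 0.05, and no Tukey adjustment.

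| ρ | Power, concentration ANOVA | Power, fold-increase ANOVA | Power, ANCOVA |
|---|---|---|---|
| 0.5 | 0.60 | 0.60 | 0.72 |
| 0.7 | 0.60 | 0.81 | 0.87 |

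**Step 3: a chance baseline difference.** Suppose one group starts 0.1 log10 higher. With s = 0.4 the standard error of the baseline difference is 0.4 × √(2/50) = 0.08, so this is 1.25 standard errors. The estimated ratio is multiplied by 10^(0.1ρ) for concentration ANOVA, which is 1.07 to 1.23 over ρ = 0.3 to 0.9. For fold-increase ANOVA the factor is 10^(−0.1(1 − ρ)), which is 0.85 to 0.98. The two readings move in opposite directions and always differ by 10^0.1 = 1.26.

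**Step 4: ANCOVA removes the ambiguity.** Write y for log Day 30, x for log Day 0 and g for group. If y = a + b·g + c·x, then y − x = a + b·g + (c − 1)·x. The group contrast b is the same for either outcome; the simulation confirmed this in every run. It holds for IgG because the general rule in section 11.2.4 gives values below the cut-off half the cut-off for both GMC and fold increase. The differing rules there apply only to RSV-A and RSV-B neutralisation.

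**The case against.** The strongest reply is that the intended outcome can be recovered. The model sentence refers back to fold increases, Template 53 has GMF columns and a GMF ratio, and its N counts subjects with a pre-vaccination result. This stands: fold increase is the likely intention. The model sentence and the footnote still say concentration, so the text needs correcting.

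A reader might infer that the analysis ignores baseline altogether. On the fold-increase reading it does not, because Day 0 enters through the ratio. What is missing is the covariate.

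A reader might also infer systematic bias, for instance from regression to the mean. The documents do not support that: groups are randomised and the subset is random, so both ANOVA readings are unbiased over repeated randomisation. The shifts in step 3 are conditional on an observed imbalance, and the ANOVA interval already allows for that variation. At ρ = 0.5, a baseline difference of one standard error (0.20 SD) shifts the fold-increase contrast by 0.10 SD. That is half of its standard error, √(2/50) × √(2(1 − 0.5)) = 0.20 SD.

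The size of the gain is assumed, and at ρ = 0.9 it is only 5% against fold-increase ANOVA. That also stands.

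Finally, the unadjusted GMF ratio has the merit of equalling the ratio of the fold increases tabulated by group; an adjusted ratio generally will not.

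**Conclusion.** The point holds as a mismatch between target and stated outcome, together with an avoidable loss of efficiency. With equal variances, ANCOVA has lower residual variance than either reading for any correlation strictly between 0 and 1. Against the likely intended reading the saving is about 5 to 35% for ρ from 0.9 down to 0.3. Correlation, SD, true ratio and size of imbalance are all assumptions.

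The consequences are limited. The comparison is labelled exploratory and runs in a subset, and section 7 calls all comparative analyses descriptive. It would be wrong to infer that the primary ranking is affected: IgG Total and IgG1 are not among the four desirability endpoints in section 6.4.2. Nor do all other assays use ANCOVA between groups. That applies to neutralising titres and PCA; anti-neogenin has no between-group model. The change is worth making because it uses data already collected and settles the wording at the same time.

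**What to change.** In section 6.2.2, replace the model sentence with:

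*ANCOVA on log10 Day 30 concentration (equivalently log10 fold increase) with vaccine group and log10 Day 0 concentration, with age group and centre if deemed necessary as in 6.2.1.2; the back-transformed group contrast is reported as the baseline-adjusted ratio of fold increases.*

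In Template 53, change ANOVA to ANCOVA and make the footnote name the baseline-adjusted fold-increase ratio instead of the concentration. Log10 Day 0 is the essential addition; age group and centre keep the conditional status they have in 6.2.1.2.

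The cost is small. Template 53 runs on %GMF_RATIO, whereas the RSV-A ratio table uses %GMT_RATIO, so the former must be adapted and checked. The adjusted ratio will not exactly equal the ratio of the tabulated within-group fold increases, and a footnote should say so. No subjects are lost, since anyone without a Day 0 value has no fold increase either. If the sponsor prefers the unadjusted analysis, the minimum correction is to name log10 fold increase as the outcome in both places.

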6.3. Analysis of safety

6.3.1. Analysis of safety planned in the protocol

The analysis of safety will be performed on the ES.

6.3.1.1. Within group analysis

The percentage of subjects with at least one **local AE** (solicited and unsolicited), with at least one **general AE** (solicited and unsolicited) and with any AE during the 7-day or 30-day follow-up period after vaccination will be tabulated with exact 95% CI. The same computations will be done for \geq Grade 2 and Grade 3 AEs, for any AEs considered related to vaccination, for any Grade 3 AEs considered related to vaccination and for AEs resulting in medically attended visit.

The percentage of subjects reporting each individual **solicited local AE** (any grade, \geq Grade 2, Grade 3, resulting in medically attended visit) during the 7-day follow-up period after vaccination will be tabulated for each study vaccine for each group. The percentage of subjects reporting each individual **solicited general AE** (any grade, \geq Grade 2, Grade 3, any related, \geq Grade 2 related, Grade 3 related, resulting in medically attended visit) during the 7-day follow-up period after vaccination will be tabulated for each group.

For fever during the 7-day follow-up period after vaccination, the number and percentage of subjects reporting fever will be reported by half degree ($^{\circ}\text{C}$) cumulative increments. Similar tabulations will be performed for causally related fever, Grade 3 ($> 39.5^{\circ}\text{C}$) causally related fever and fever resulting in a medically attended visit. In addition, the prevalence of any and Grade 3 fever will be presented graphically over time after vaccination.

The percentage of subjects with any **unsolicited** symptoms within 30 days after vaccination with its exact 95% CI will be tabulated by group and by Medical Dictionary for Regulatory Activities (MedDRA) preferred term. Similar tabulation will be done for Grade 3 unsolicited symptoms, for any causally related unsolicited symptoms, for Grade 3 causally related unsolicited symptoms and for unsolicited symptoms resulting in a medically attended visit (The verbatim reports of unsolicited symptoms will be reviewed by a physician and the signs and symptoms will be coded according to the MedDRA

Dictionary for Adverse Reaction Terminology. Every verbatim term will be matched with the appropriate Preferred Term).

SAEs reported throughout the study will be described in detail.

Pregnancy exposures throughout the study and pregnancy outcomes will be described in detail (if applicable).

The percentage of subjects using **concomitant medication** (any medication, any antipyretic and any antipyretic taken prophylactically) during the 7-day (Day 0 to Day 6) or 30-day (Day 0 to Day 29) follow-up period after vaccination will be summarised by group.

For all subjects in each group and each **haematology and biochemistry** parameter:

- The percentage of subjects having haematology and biochemistry results below or above the local laboratory normal ranges will be tabulated for each timepoint.
- The maximum grading post-vaccination (from Day 7 to Day 90) versus baseline (Day 0) and the percentage of subjects with laboratory parameters above or equal to Grade 1, Grade 2, Grade 3 and Grade 4 will be tabulated (Grades will be based on the FDA Guidance for Industry “Toxicity Grading Scale for Healthy Adult and Adolescent Volunteers Enrolled in Preventive Vaccine Clinical Trials”, see APPENDIX D of the Protocol: FDA toxicity grading scale. Those laboratory parameters not included on FDA Toxicity Grading Scale will not be graded).

Assessment of anti-NEO immune response at Day 30 post-vaccination for each group:

- GMCs pre-and post-vaccination will be tabulated with 95% CI and represented graphically.
- Individual post-vaccination *versus* pre-vaccination results will be plotted using scatter plots. Results of the control group will be used as a reference.
- Geometric mean of ratios of antibody concentrations at Day 30 over pre-vaccination will be tabulated with 95% CI.
- Distribution of the antibody concentrations pre-and post-vaccination and of fold increase after vaccination will be tabulated.

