3.2. Secondary objectives

- To evaluate the reactogenicity and safety of a single intramuscular dose of the RSV investigational vaccines up to study conclusion.
- To evaluate the immunogenicity of a single intramuscular dose of the RSV investigational vaccines up to 90 days after vaccination (Day 90).
- To further assess the safety of the investigational RSV vaccines by evaluating whether a single dose of the vaccines induces antibodies against the residual host cell protein neogenin (NEO) up to 1 month post-vaccination (Day 30).
- To estimate the incidence of medically attended RSV-associated RTIs up to study conclusion.

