4.2. Secondary

- Occurrence of AEs from vaccination up to study conclusion:
 - Occurrence of each solicited local and general AE, during a 7-day follow-up period after vaccination (i.e. the day of vaccination and 6 subsequent days), for all subjects in all groups;
 - Occurrence of any unsolicited AE, during a 30-day follow-up period after vaccination (i.e. the day of vaccination and 29 subsequent days), for all subjects in all groups;
 - Occurrence of any haematological (haemoglobin level, White Blood Cells [WBC], lymphocyte, neutrophil, eosinophil and platelet count) and biochemical (alanine amino-transferase [ALT], aspartate amino-transferase [AST] and creatinine) laboratory abnormality at Day 0, Day 7, Day 30, Day 60 and Day 90 for all subjects in all groups;
 - Occurrence of any SAE, for all subjects in all groups.
- Functional antibody titres against RSV for all subjects in all groups:
 - Neutralising antibody titres against RSV-A at Day 0, Day 30, Day 60 and Day 90;
 - Neutralising antibody titres against RSV-B at Day 0, Day 30, Day 60 and Day 90.
- PCA concentration at Day 0, Day 30, Day 60 and Day 90 for all subjects in all groups.
- Humoral immune response to the residual host cell protein NEO in the investigational RSV vaccine at pre-vaccination (Day 0), and 1 month post-vaccination (Day 30) for all subjects in all groups.
 - Antibody concentrations against NEO
- Occurrence of medically attended RSV-associated RTIs up to study conclusion

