11.2.4. Immunogenicity

- For a given subject and given immunogenicity measurement, missing or non-evaluable measurements will not be replaced. Therefore, an analysis will exclude subjects with missing or non-evaluable measurements.
- A seronegative subject is a subject whose antibody titre/concentration is below the cut-off value of the assay. A seropositive subject is a subject whose antibody titre/concentration is greater than or equal to the cut-off value of the assay.
- The Geometric Mean Concentrations/Titres (GMC/Ts) calculations are performed by taking the anti-log of the mean of the log titre transformations. Antibody titres below the cut-off of the assay will be given an arbitrary value of half the cut-off of the assay for the purpose of GMT calculation. The cut-off value is defined by the laboratory before the analysis and is described in the protocol.
- In order to compute fold increase of antibody titres/concentrations (ratio) between post-vaccination and pre-vaccination titres/concentrations and for GMC/GMT calculation, antibody titres/concentrations below the assay cut-off will be given an arbitrary value of half the cut-off.
- *The cut-off for the updated (qualified) version of the PCA assay will be set at the level of the assay LLOQ (9.60 µg/mL). For results below the cut-off (LLOQ), an arbitrary value of half of the cut-off will be considered for calculation of GMC and fold increase.*
- *Considering cut-offs or neutralising antibody against RSV-A and RSV-B are below the assays' LLOQ, the following rules will be applied:*

Assay	Raw result	Derivation for seropositivity status	Derivation for GMT calculation	Derivation for fold-increase between Post and Pre-vaccination titres
Neutra RSV-A	<8	NEG	4	LLOQ/2
	[8-LLOQ[POS	8	LLOQ/2
	≥LLOQ	POS	Exact value	Exact value
Neutra RSV-B	<6	NEG	3	LLOQ/2
	[6-LLOQ[POS	6	LLOQ/2
	≥LLOQ	POS	Exact value	Exact value

- *Vaccine response to the RSV neutralising antibodies (anti-RSV-A and anti-RSV-B) will be defined as:*
 - *At least a 4-fold increase from pre-vaccination if pre-vaccination neutralising antibody titre <7 log₂ (<128).*
 - *At least a 3-fold increase from pre-vaccination if pre-vaccination neutralising antibody titre in [7-8] log₂ ([128-256]).*
 - *At least a 2.5-fold increase from pre-vaccination if pre-vaccination neutralising antibody titre in >8-10 log₂ (>256-1024).*

- *At least 1-fold from pre-vaccination if pre-vaccination neutralising antibody titre >10 log₂ (>1024).*

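### The SAP asks whether the vaccine induces anti-neogenin antibodies but plans no estimate against placebo, and its half-cut-off rule scores every upward crossing of the cut-off as at least a 2-fold rise

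*SAP*

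**What the plan says.** All references are to SAP Amendment 4.

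- **Objective (3.2).** "To further assess the safety of the investigational RSV vaccines by evaluating whether a single dose of the vaccines induces antibodies against the residual host". The protein in question is neogenin, and the horizon is Day 30.
- **Endpoint (4.2).** Anti-NEO concentrations are measured at Day 0 and "1 month post-vaccination (Day 30) for all subjects in all groups". Control is one of four randomised groups of about 100 (Section 2).
- **Analysis (6.3.1.1, a within-group section).** Under "Assessment of anti-NEO immune response at Day 30 post-vaccination for each group" the SAP lists pre and post GMCs with 95% CI, scatter plots with Control as a reference, the geometric mean of Day 30/Day 0 ratios ("Geometric mean of ratios of antibody concentrations at Day 30 over pre-vaccination will be tabulated with 95% CI"), and distributions of concentration and of fold increase. Section 6.2.1.1 sets the fold thresholds: "For antibody concentrations against NEO: percentage of subjects with a fold increase equal to or above 1, 1.5, 2, 2.5" and onward to 5.
- **Displays (Annex 4).** Templates 41 (concentrations) and 42 (fold) have rows for each group, Control included.
- **Between-group sections.** 6.2.1.2 compares neutralising titres and PCA among the RSV vaccine groups only. 6.3.1.2 compares vaccine with placebo, but only for percentages with adverse events, fever or related SAEs. Neither mentions NEO.
- **Low values (11.2.4).** For GMCs and fold increases, "antibody titres/concentrations below the assay cut-off will be given an arbitrary value of half the cut-off". NEO is not excepted. The section leaves the cut-off itself to the laboratory and the protocol. Template 41 has its lowest boundary at 55 ng/mL but does not call it the cut-off.

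**The concern.** Whether a dose induces an antibody is a causal question. A change from Day 0 to Day 30 within a vaccinated group combines any vaccine effect with assay drift and measurement noise. Control carries the same drift and noise, so the direct answer is the vaccine-to-Control contrast with its own interval. The SAP gives neither that contrast nor a criterion for calling antibodies induced. Section 6.4 names the Section 6.3 analyses, which include NEO, among the evidence for choosing a formulation, so the answer has a use beyond description.

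The second issue concerns reading the fold table. If results just under the cut-off are common, ordinary noise will place subjects in the 2-fold column of a safety table. The same substitution can hide real rises among subjects who start well below the cut-off.

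**Working it through.** The SAP gives no sample size, expected rate or precision for NEO, so there is no planned figure to reproduce.

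**1. Effect of the half-cut-off rule.** Let the cut-off be c. A Day 0 result below c becomes c/2, and a Day 30 result at or above c is kept. The scored ratio is then at least c ÷ (c/2) = 2 for any c. By the same argument a downward crossing scores at most 0.5.

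Taking c = 55 ng/mL (an assumption from Template 41), so that c/2 = 27.5:

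| Day 0 → Day 30 (ng/mL) | Real ratio | Scored ratio |
|---|---|---|
| 54 → 56 | 1.04 | 56/27.5 = 2.04 |
| 50 → 55 | 1.10 | 55/27.5 = 2.00 |
| 40 → 60 | 1.50 | 60/27.5 = 2.18 |
| 20 → 56 | 2.80 | 56/27.5 = 2.04 |
| 56 → 54 | 0.96 | 27.5/56 = 0.49 |

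Small upward crossings are exaggerated and a large one is shrunk.

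**2. How often, if nothing changes.** Simulation of 400,000 pairs. All inputs are assumptions: c = 55, lognormal values, between-subject SD 0.3 log10, baseline medians of 20, 35, 55 and 80 ng/mL, and three within-subject SDs per sample.

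| Within-subject SD (log10) | Scored ≥2-fold under the rule | ≥2-fold on raw values |
|---|---|---|
| 0.05 | 1.3% to 3.8% | 0.0% |
| 0.10 | 2.7% to 7.7% | 1.6% to 1.7% |
| 0.15 | 4.4% to 12.6% | about 7.8% |

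At SD 0.15 and median 20 the rule gives fewer false 2-fold rises than raw values (4.4% against 7.8%). Across all these settings the geometric mean ratio stays between 0.999 and 1.001, because upward and downward crossings offset.

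**3. Attenuation of a real rise.** Same model with within-subject SD 0.10. A true 2-fold rise in every subject gives a geometric mean ratio of 1.08, 1.35 and 1.75 at baseline medians of 10, 20 and 35 ng/mL.

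**4. Precision of a contrast with Control.** The 95% CI factor is 10^(1.96 × SD × √(2/n)), with n = 100 per group and SD that of the log10 fold (assumed).

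- SD 0.1: 10^(1.96 × 0.1 × 0.1414) = 1.07
- SD 0.2: 1.14
- SD 0.3: 1.21

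Power to detect a 1.2-fold ratio to Control is above 0.99, 0.80 and 0.46 respectively. The no-change simulations gave SDs of the substituted log10 fold between 0.06 and 0.25, so the assumed range is compatible with them.

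**The case against.** **Control is not ignored.** It has its own rows in Templates 41 and 42 and is the scatter-plot reference. Every by-group GMC and geometric mean ratio is produced for it under the same substitution rule. Drift and cut-off noise can therefore be read beside the vaccine groups, and an unadjusted ratio could be worked out by hand from the by-group ratios and intervals. This stands: what is missing is a stated, baseline-adjusted contrast with its own interval.

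**All comparisons are descriptive (Section 7).** True, but 6.3.1.2 already defines exploratory vaccine-minus-placebo contrasts with 95% CIs for adverse events, so a NEO contrast fits the plan's own framework.

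**Nothing makes the 2-fold column decisive.** Also true. A reader might infer that induction is judged from fold rises alone. The SAP lists GMCs and concentration distributions as well and names no threshold.

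**The geometric mean ratio is sound under no change.** This stands. A reader might infer that the substitution inflates it, but step 2 shows that it does not. The artefact of false rises is confined to the fold distribution.

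**The NEO templates showing Day 60 and Day 90.** Template 51 carries the note "This graph will display the 4 groups and the 4 immuno timepoints: PRE, PI(D30), PI(D60) and PI(D90", and Templates 41 and 42 have the same later timepoints, while the objective, endpoint and analysis text stop at Day 30. A reader might infer a real conflict over sampling. Annex 4 says the mock displays are illustrative and will be adapted, so this is carry-over and adds no weight.

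**Conclusion.** The point holds in two parts. First, the SAP poses a causal safety question, has a randomised placebo group with the required samples, and plans no vaccine-versus-placebo NEO estimate with a CI. This rests on the text alone. Second, every upward crossing of the cut-off scores at least 2-fold in the fold distribution. This is arithmetic and does not depend on the value of the cut-off.

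The size of the second part is not established. It depends on the cut-off (55 ng/mL is only inferred), the baseline distribution and the assay noise, none of which the SAP gives. The 1.3% to 12.6% range is illustrative. A reader might infer that false 2-fold rises affect up to a quarter of subjects. With an assumed CV of 15% to 25%, rates of 8% to 25% do arise, but only among subjects whose true level is 45 to 54 ng/mL, just under the assumed cut-off. The SAP does not show how many such subjects there are.

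Nor do the documents support saying that a vaccine effect could not be told from noise. Control carries the same artefact and is shown. This is a worthwhile, inexpensive improvement to a safety analysis, not a flaw that invalidates it.

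**What to change.** 1. **Add to 6.3.1.2, as exploratory and descriptive, on the Exposed Set:**
   - the Day 30 anti-NEO GMC ratio of each PreF group to Control with 95% CI, from an ANCOVA of log10 concentration on group and Day 0 value. Report the percentage below the cut-off beside it, and state that the ratio is attenuated if that percentage is high, because the model uses the same substituted values;
   - the difference from Control in the percentage going from below to at or above the cut-off, with the denominator stated, using the standardised asymptotic 95% CI already specified in 11.1.
2. **Name the analyses that will report these contrasts.** Section 9 drops the existing adverse-event contrast table from the final analysis, so placement in 6.3.1.2 alone would leave this unclear.
3. **Stratify Template 42 by Day 0 status.** Keep fold categories for subjects at or above the cut-off at Day 0. Show the others as remained below or crossed, with the Day 30 concentration category so that the size of the rise is kept.
4. **State the NEO cut-off in 11.2.4**, as is done for PCA and the neutralisation assays.
5. **Editorial only:** remove Day 60 and Day 90 from Templates 41, 42 and 51.

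The cost is SAP wording, one extra table and three more exploratory contrasts per measure, which the multiplicity caution in Section 7 already covers. No new samples or assays are needed.
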